7.1.2. Geometric Mean Fold Rise (GMFR)

Unadjusted and adjusted GMFRs will be calculated similarly as the unadjusted and adjusted GMTs.

7.1.3. Geometric Mean Ratio (GMR)

For each subject and visit, the ratio of serum anti-RSV/A versus RSV/B and serum anti-hMPV/A versus hMPV/B titers and fold-rises will be calculated to determine the GMR of titers and fold-rises.

The unadjusted geometric mean ratio (GMR) and 95% CIs of the titers and fold-rise for serum anti-RSV/A versus RSV/B and serum anti-hMPV/A versus hMPV/B will be calculated similarly to the unadjusted GMTs. The adjusted GMRs and 95% CIs will be calculated, similarly to the adjusted GMT models. The log2 transformed baseline titers will be included as the continuous covariates.

This document is confidential.

For each subject and visit, the ratio of fold-rise in IgG prefusion F protein-specific antibody titers versus the fold-rise in the corresponding Nab titers of serum anti-RSV/A or hMPV/A will be calculated to determine the GMR.

The unadjusted GMR and 95% CIs of the fold-rise in IgG prefusion F protein-specific antibody titers versus the fold-rise in the corresponding Nab titers of serum anti-RSV/A or hMPV/A will be calculated similarly to the unadjusted GMTs. The adjusted GMRs and 95% CIs will be calculated, similarly to the adjusted GMT models. The log2 transformed baseline titers will be included as the continuous covariates.

7.1.4. Baseline Tertiles

Baseline tertiles are defined as follows: first tertile is <=33.3rd percentile, second tertile is >33.3rd - <=66.7th percentile, and third tertile is >66.7th percentile.

When summarizing by age subgroup category, baseline tertiles are defined as follows: first tertile is <=33.3rd percentile, second tertile is >33.3rd - <=66.7th percentile, and third tertile is >66.7th percentile by total arm within each age subgroup category.

7.1.5. Reverse Cumulative Distribution Curves (RCDCs)

Reverse cumulative distribution curves (RCDCs) for assays (on a log scale for x-axis) for a combination of available time points and vaccine groups will be generated.

7.1.6. Tukey Method for Outlier Detection

Tukey's method for outlier detection will be implemented whereby datapoints either below $Q1 - 1.5IQR$ or above $Q3 + 1.5IQR$ are flagged. (Q1 and Q3 represent the 25th and 75th percentile of the data, respectively. IQR represents the width of the interquartile range). When utilizing the Tukey Method, the datapoints, including the boundaries, will be calculated using the log2 transformed values. The outliers and boundaries will be back-transformed for presentation.

7.1.7. Immunogenicity Titers and Concentrations below LLOQ or above ULOQ

Antibody titers and concentrations below the LLOQ will be set to LLOQ before performing the conversion, as described in [section 7.1](#), for GMT/GMFR calculations. Antibody titers and concentrations above the ULOQ will be set to ULOQ before performing GMT/GMFR calculations. Methods of computation involving LLOQ and ULOQ are described in [section 7.1](#).

7.2. Key Definitions

Baseline

Unless otherwise specified, Baseline is defined as the last available value prior to the first administration of IVX-A12 vaccine (or placebo) and includes assessments taken on Day 0 (Study Day 1).

Change from baseline

The change from baseline will be calculated for each post-baseline assessment as:

Change from Baseline = Post-baseline value - Baseline value

This document is confidential.

Fold Change from baseline

The fold change from baseline will be calculated for each post-baseline assessment as:

Fold change from Baseline = Post-baseline value / Baseline value

Study Day

Study day is calculated as (event date – vaccination date + 1) if event date \geq vaccination date; and (event date – vaccination date) if event date $<$ vaccination date.

7.3. Missing Data

This section will describe the handling of missing data and partial/missing dates.

7.3.1. Safety Data

Missing date imputation will be applied to prior and concomitant medications and adverse events as described in [Table 2](#).

Table 2: Imputation Rules for Missing Start/Stop Dates

Partial Missing Start or Stop Date	Imputed Start Date	Imputed Stop Date
Date is completely missing	Impute the date as dose date	If the status is ongoing then do not impute, i.e., leave the end date missing; if the status is not ongoing, then impute the date as the study end reference date
Missing month and day, and the year is present	If the year is the same as the year of dose date, then impute day and month same as dose day and month; If the year is different with dose year, then use January 1	If the year is the same as the year of the study end reference date, then impute the day and month same as the day and month of the study end reference date; If the year is different from the year of study end reference date, then use December 31
Missing day, but year and month are present	If the year and month are the same as the year and month of dose date, then impute the date same as dose date; If Year or month are different with than dose year or month, then impute the date as first day of that month	If the year and month are the same as the year and month of the study end reference date, then impute the day same as the day of the study end reference date; If the year or month is different from the year or month of the study end reference date, use the last day of the month.

This document is confidential.

Missing month, but year and day are present	If year is the same as dose year than then impute the month same as dose; If Year is different with dose year, than then impute the month as January	If the year is the same as the year of study end reference date, then impute the month same as the month of study end reference date; If the year is different from the year of study end reference date, then impute the month as December.
---	---	---

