8.1.5. Medication

All medications will be coded using the World Health Organization Drug Dictionary (WHO-DD) Format B3 Version March 2023.

Prior medications are defined as any medications taken before trial dose administration, regardless of whether it was stopped prior to the trial dose administration. Concomitant medications are defined as any medications with start date or stop date on or after the trial dose administration until the end of the main trial. The prior and concomitant medications will be summarized separately.

This document is confidential.

For the purposes of classifying medications into prior/concomitant, the algorithms in [section 7.3.1](#) will be used for imputing missing dates.

Medications will be summarized by Anatomical Therapeutic Chemical (ATC) Level 4 and PT. If ATC Level 4 is missing, the next higher non-missing ATC Level will be used. For each medication, the number and percentage of subjects will be displayed for the Safety Set by vaccine group, IVX-A12 aggregate, and overall. The tables will be sorted by overall descending frequency of ATC Level 4 and then, within an ATC Level, by overall descending frequency of PT in the total column. If a subject has one or more medications more than once, the subject is counted only once under any given ATC Level 4 or PT.

All prior and concomitant medications, up to the end of the main trial, will be listed for the Safety Set.

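### SAP Table 2 imputes medication start dates without checking the recorded stop date, so a drug stopped before vaccination can be counted as concomitant and an ongoing drug of unknown start can miss the prior-medication table

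*SAP*

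**What the plan says.** SAP 7.3.1 gives a single table for both data types: "Missing date imputation will be applied to prior and concomitant medications and adverse events as described in" Table 2. Its start-date column contains these rules:

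- Date completely missing: "Impute the date as dose date".
- Only the year known: "If the year is the same as the year of dose date, then impute day and month same as dose day and month"; otherwise 1 January of the stated year.
- Year and month known: "If the year and month are the same as the year and month of dose date, then impute the date same as dose date"; otherwise the first of that month.

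In the stop-date column, an ongoing record keeps a missing stop. For a completely missing stop, "if the status is not ongoing, then impute the date as the study end reference date".

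SAP 8.1.5 defines the two classes and tabulates them separately. "Prior medications are defined as any medications taken before trial dose administration, regardless of whether it was stopped prior to the trial dose administration". A concomitant medication is one whose start or stop falls at or after dosing, up to the end of the main trial. "For the purposes of classifying medications into prior/concomitant", the section points back to the 7.3.1 algorithms.

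**The concern.** Setting an unknown start to the dose date is a conservative choice for an adverse event, because the event is then counted as post-vaccination. For a medication the same rule works differently. It can assert that a drug began on the day of vaccination when the record shows that it had already stopped, and it can remove evidence of treatment present at baseline.

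Such records are plausible in this trial. Protocol 7.1 admits adults aged 60 to 85 with stable chronic conditions. Protocol 9.1.2 collects medications from 1 month before screening, and Protocol 2.1 allows screening up to 28 days before dosing. Drugs stopped before Day 0 will therefore be in the database. At stake is whether the prior table describes baseline treatment correctly, and whether the concomitant table contains only drugs that could have been taken after vaccination.

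**Working it through.** The SAP gives no figure to reproduce, so the check applies its rules literally to test records.

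**Notation.** D is the dose date, S the start after Table 2, and E the stop after Table 2.

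**Classification.**
- Concomitant if S ≥ D or E ≥ D (SAP 8.1.5).
- Prior if S < D. This is an operational reading. SAP 8.1.5 speaks of drugs taken before dosing and does not name the start date.

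**Assumed dates.** D = 15 Jul 2023 and study end = 15 Jul 2024, for illustration only. The results depend on the order of the dates, not on these values.

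| # | Recorded start | Recorded stop | S | E | Prior (S < D) | Concomitant |
|---|---|---|---|---|---|---|
| 1 | unknown | ongoing | 15 Jul 2023 | missing | no | yes |
| 2 | unknown | 1 Jul 2023 | 15 Jul 2023 | 1 Jul 2023 | no | yes |
| 3 | unknown | unknown, not ongoing | 15 Jul 2023 | 15 Jul 2024 | no | yes |
| 4 | 2010 | ongoing | 1 Jan 2010 | missing | yes | no |
| 5 | 2010 | 1 Jul 2023 | 1 Jan 2010 | 1 Jul 2023 | yes | no |
| 6 | 2023 | ongoing | 15 Jul 2023 | missing | no | yes |
| 7 | 2023 | 1 Mar 2023 | 15 Jul 2023 | 1 Mar 2023 | no | yes |
| 8 | Jul 2023 | 10 Jul 2023 | 15 Jul 2023 | 10 Jul 2023 | no | yes |

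**Reading the table.**

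- Records 2, 7 and 8 have S > E, which is impossible. In record 2 the drug stopped 14 days before dosing (15 − 1 = 14). Because S = D satisfies S ≥ D, each is concomitant despite a recorded stop before dosing. This follows directly from the stated rules.
- Records 1, 3 and 6 leave the prior table only if prior status is decided by S < D.
- Records 4 and 5 mark the limit. A known earlier year gives a pre-dose start and the drug stays prior.
- Record 4 also shows a separate gap that matters for the repair. An ongoing drug with a pre-dose start has no stop date after Table 2, so it meets neither limb of the concomitant definition.

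**The case against.** The strongest objection concerns scope. A reader might infer that long-standing drugs in general disappear from the prior table. The documents do not support that: an earlier known year is set to 1 January of that year, an earlier known month to its first day, and the drug remains prior. A start known only to lie in the dose year is not evidence of a long-standing drug. The loss is confined to completely unknown starts and to partial dates matching the dose year or month.

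A second objection is about wording. Because SAP 8.1.5 defines prior use as use before dosing, a drug with a recorded pre-dose stop arguably stays prior whatever its imputed start. That stands. For records 2, 7 and 8 the firm error is therefore the false concomitant entry, and absence from the prior table depends on how the definition is programmed.

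Third, a reader might attach a percentage to the problem or say that every missing start is misdated. The documents give no rate of missing dates, and some drugs of unknown start may really have begun on or after dosing.

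Fourth, the reporting is partly transparent. SAP 8.1.5 lists all prior and concomitant medications, and SAP 13.2.5.3 shows missing parts of dates as dashes, so an unknown start is visible in the listing. Medical history is tabulated separately (SAP 8.1.3). This limits the harm but does not correct the tables.

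Finally, simply moving unknown starts to before dosing is not harmless. As record 4 shows, an ongoing drug would then literally drop out of the concomitant table. That stands, and it shapes the fix.

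**Conclusion.** The point holds in limited form. Table 2 never compares an imputed medication start with the recorded stop, and SAP 8.1.5 relies on the result, so a drug stopped before vaccination can be reported as concomitant. This is a stated rule giving a wrong answer, not missing detail. Omission of ongoing drugs of unknown start from the prior table is conditional on prior status being programmed from the imputed start date.

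The number of affected records cannot be derived from the documents. The effect is confined to descriptive Safety Set medication tables. A reader might infer some effect on the trial's conclusions, but no endpoint or immunogenicity model uses the prior/concomitant class, and PPS membership rests on major deviations and data points judged at the blinded data review (SAP 6.1.5). It is a low-priority correction worth making because it is cheap.

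**What to change.** Keep the dose-date rule for adverse events and add the following for medications:

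1. In SAP 7.3.1, never impute a start later than a recorded stop. In SAP 8.1.5, do not class a drug as concomitant when its recorded stop is before dosing.
2. Class a medication of unknown start as prior unless the known part of its start date, or the way it was recorded, shows that it began on or after dosing.
3. Extend the concomitant definition in SAP 8.1.5 to drugs ongoing at or after dosing, so that ongoing drugs with a pre-dose or unknown start appear in both tables.

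Under these rules, and with nothing else on record about when the drug began, records 1, 3, 4 and 6 become both prior and concomitant, and records 2, 5, 7 and 8 become prior only. Item 3 has to accompany item 2; otherwise ongoing chronic drugs would be lost from the concomitant table.

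The cost is a few sentences across two SAP sections and a small programming change. The downside is small: a few drugs of unknown start that in fact began after dosing may also appear as prior.

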10.1.1. Adverse Events

Adverse events are collected as solicited, unsolicited AEs, SAEs, CESIs, and MAAEs. Solicited ARs are recorded in the subject diary; unsolicited AEs are collected on AE page of case report forms (CRFs). Furthermore, a solicited ARs that is ongoing after the diary period, leads to trial discontinuation, or results in an MAAE or SAE, should be entered on the AE page of the CRF as an unsolicited AE. The following are primary endpoints: Solicited local reactions and systemic ARs from the day of dosing (Day 0) through Day 6 (Study Day 1 to Study Day 7); Unsolicited AEs from day of dosing (Day 0) through 28 days post-vaccination (Study Day 1 to Study Day 29). SAEs, MAAEs and AEs leading to trial withdrawal from day of dosing (Day 0; Study Day 1) up to the end of the main trial, CESIs (mild, moderate or severe lower respiratory tract infection (LRTI) caused by RSV and/or hMPV) from day of dosing (Day 0; Study Day 1) up to the end of the main trial, and AESIs (including anaphylaxis, thrombocytopenia, and pIMCs, including Guillain Barre's syndrome, as defined in [section 16](#)) are secondary safety endpoints. AE summaries will be performed on the Safety Set, unless otherwise stated.

An overall summary of the number and percentage of subjects reporting any solicited ARs, Grade 3 solicited ARs, Grade 4 solicited ARs, \geq Grade 3 solicited ARs any unsolicited AEs, trial vaccine-related unsolicited AEs, Grade 3 unsolicited AEs, Grade 3 trial vaccine-related AEs, Grade 4 unsolicited AEs, Grade 4 trial vaccine-related AEs, \geq Grade 3 unsolicited AEs, \geq Grade 3 unsolicited AEs, SAEs, trial vaccine-related SAEs, CESIs, trial vaccine-related CESIs, AESIs (including pIMCs), trial vaccine-related AESIs (including pIMCs), MAAEs, trial-vaccine related MAAEs, AEs leading to trial discontinuation and AEs leading to death will be provided. The summary will be repeated by vaccine group and age subgroup analyses category.

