A separate summary of the number and percentage of subjects reporting any AEs leading to main trial discontinuation, trial vaccine-related AEs leading to main trial discontinuation, SAEs leading to main trial discontinuation, trial vaccine-related SAEs leading to main trial discontinuation, CESIs leading to main trial discontinuation, trial vaccine-related CESIs related to main trial discontinuation, AESIs leading to main trial discontinuation, trial vaccine-related AESIs leading to main trial discontinuation, and MAAEs leading to main trial discontinuation, trial vaccine-related MAAEs leading to main trial discontinuation will also be provided. The summary will be repeated by vaccine group and age subgroup analyses category.

Listings will be provided for solicited ARs, unsolicited AEs, SAEs, CESIs, AESIs, MAAEs, non-RSV/hMPV LRTIs and AEs leading to main trial discontinuation for all data up to the end of the main trial. The listings will display study day, which is calculated as (event date – vaccination date + 1) if event date \geq vaccination date; and (event date – vaccination date) if event date $<$ vaccination date. AEs starting prior to the vaccination will be listed only and not included in summaries. A listing of solicited ARs, possibly reported incorrectly as unsolicited ARs, will also be included. If the solicited AR, possibly reported as an unsolicited AR, has a severity that is discrepant from the pre-defined diary, the discrepancy will also be reported.

This document is confidential.

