10.1.1.2. Unsolicited Adverse Events

An unsolicited AE is an AE that was not solicited using the post-vaccination diary and that was spontaneously communicated by a subject. Unsolicited AEs will be collected for 28 days following the administration of the vaccination. Any solicited AR observed as continuing Day 7 following trial vaccination will be additionally recorded as an unsolicited AE.

Unsolicited AEs will be classified by system organ class (SOC) and preferred term (PT) according to MedDRA version 26.0 or greater.

The severity of AEs is determined by the investigator as Mild (Grade 1), Moderate (Grade 2), Severe (Grade 3), and Potentially Life-threatening (Grade 4). If there are events with missing severity, the category 'Missing' will be summarized separately from the non-missing categories.

The relationship (causality) of AE to the vaccine will be assessed by the investigator as Related and Not Related. If there are events with missing relationship, the category 'Missing' will be summarized separately from the non-missing categories.

Any solicited AR reported incorrectly as an unsolicited AE, as determined by the Icosavax medical lead, will be included in the unsolicited adverse event summaries and listings.

Unsolicited AEs will be summarized as below by vaccine group, aggregate IVX-A12, and overall:

This document is confidential.

- The number and percentage of subjects reporting unsolicited AEs by SOC and PT.
- The number and percentage of subjects reporting unsolicited AEs by SOC, PT and maximum severity.
- The number and percentage of subjects reporting \geq Grade 3 unsolicited AEs by SOC and PT.
- The number and percentage of subjects reporting vaccine-related unsolicited AEs by SOC and PT.
- The number and percentage of subjects reporting \geq Grade 3 and vaccine-related unsolicited AEs by SOC and PT.

All above summaries will be repeated by age subgroup analyses category.

Summaries will be ordered by descending frequency of SOC, and then within each SOC, by overall descending frequency of PT in the total column. If a subject has one or more unsolicited AEs more than once, the subject is counted only once under any given SOC or PT.

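### SAP Table 2 can date a post-vaccination AE with a missing start month before dosing, and so remove it from the AE-page summaries

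*SAP*

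**What the plan says.** SAP 7.3.1 brings AEs under the same rules as medications: "Missing date imputation will be applied to prior and concomitant medications and adverse events". Table 2 then has four start-date rows.

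- **Date wholly missing:** "Impute the date as dose date".
- **Month and day missing:** the dose day and month if the year is the dose year, otherwise 1 January.
- **Day missing:** "If the year and month are the same as the year and month of dose date, then impute the date same as dose date"; otherwise the first of the recorded month.
- **Month missing, day and year known:** "If year is the same as dose year than then impute the month same as dose"; if the year differs, January.

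SAP 10.1.1 gives the consequence of a start before dosing: "AEs starting prior to the vaccination will be listed only and not included in summaries". SAP 7.2 defines study day as event date minus vaccination date, plus 1 when the event is on or after vaccination.

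**The concern.** In the first three rows, an imputed start falls before dosing only when the recorded year or month already shows a pre-dose onset. A true post-dose AE always stays on or after the dose date. The missing-month row lacks that protection, because it combines the recorded day with the dose month and never compares the result with the dose date.

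The summaries exposed include a primary endpoint (unsolicited AEs, Study Days 1 to 29) and the secondary SAE, MAAE, AESI and withdrawal endpoints to Day 365. With about 100 subjects per vaccine group, the sample size section frames safety sensitivity as the chance of seeing at least one event (63.4% at 1% incidence). A single event missing from a table can therefore matter. For a true post-dose AE, dating it before dosing can only take it out of the tables.

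**Working it through.** The plan gives no figure on this point to reproduce. The check applies Table 2 literally.

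**Inputs.** Table 2 start-date rows (SAP 7.3.1), study day definition (SAP 7.2) and the pre-vaccination exclusion (SAP 10.1.1). Assumed, because the documents give no dosing calendar or onset distribution: one dose on each day of 2023, and true onset spread evenly over the stated window.

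**Worked example (assumed dates).** Dose 20 June 2023, true onset 5 July 2023, recorded as day 5, month unknown, 2023.
- True study day: 15 + 1 = 16, inside the primary window.
- Imputed start: 5 June 2023. Study day: 5 − 20 = −15.
- The AE goes to the listing only.

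**When it happens.** The true onset is in a later month of the dose year and the recorded day is earlier than the dose day. For a dose on day d of a 30-day month and onset on Days 0-28 (29 possible days), the onsets affected are days 1 to d − 2 of the next month, so the share is (d − 2)/29 for d of 2 or more:

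| Dose day | 1 | 5 | 10 | 15 | 20 | 25 | 30 |
|---|---|---|---|---|---|---|---|
| Affected | 0/29 | 3/29 | 8/29 | 13/29 | 18/29 | 23/29 | 28/29 |
| Share | 0% | 10% | 28% | 45% | 62% | 79% | 97% |

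**Over a whole year.** Share = combinations imputed before dosing ÷ all dose-onset combinations with onset in the dose year.

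| Onset window | Before dosing | Same-year combinations | Share |
|---|---|---|---|
| Days 0-6 | 231 | 2,534 | 9.1% |
| Days 0-13 | 1,001 | 5,019 | 19.9% |
| Days 0-28 | 4,438 | 10,179 | 43.6% |
| Days 0-180 | 22,422 | 49,775 | 45.0% |
| Days 0-365 | 29,277 | 66,795 | 43.8% |

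Onsets in the following year go to the January branch and cannot precede dosing. Keeping them in the denominator gives 4,438/10,585 = 41.9% for Days 0-28 and 29,277/133,590 = 21.9% for Days 0-365.

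**Other rows.** The same enumeration for the other three start-date rows gives 0 before dosing, for both Days 0-28 and Days 0-365.

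**Impossible dates.** The missing-month row also yields 1,088 combinations over Days 0-365 that are not calendar dates, such as day 31 in a 30-day month. Table 2 has no rule for them.

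**After the fix.** Setting a same-year result earlier than dosing to the dose date takes the 29,277 to 0. In the example, the start moves to 20 June (Study Day 1) and the AE returns to the summaries.

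**The case against.** **The trigger is rare.** Only the month may be unknown. Unsolicited AEs are assessed on Days 0, 3, 7, 14 and 28, start and end dates are documented for each event (Protocol 10.4.1), and SAEs, with AESIs reported as SAEs, need a form within 24 hours. Source verification and a blinded data review are also planned. This stands: few events, possibly none, will be affected, and SAEs and AESIs are the least likely.

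**The share depends on assumptions.** A reader might take 43-45% as the general figure. It needs flat onset over 28 days or more. The protocol expects most reactogenicity in the first week, and early onset brings the share down to 9-20%. This also stands.

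**The exclusion may not use the imputed date.** SAP 8.1.5 ties imputation expressly to classifying medications; SAP 10.1.1 has no matching sentence for AEs. The link is therefore inferred, but imputation is applied to AEs and no other date is named for the decision.

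**Stronger readings the documents do not support.**
- That every AE summary is affected. Solicited reactions are taken from the diary. Only the AE-page copy of a reaction continuing on Day 7 is in scope ("Any solicited AR observed as continuing Day 7 following trial vaccination will be additionally recorded as an unsolicited AE").
- That events vanish unseen. They stay in the listings with study day, and SAP 13.2.5.3 shows missing date parts as dashes.
- That the comparison between groups is biased. The rule is the same in all groups, and nothing shows a differential effect.

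**Conclusion.** The defect holds as a minor but real error in a stated rule. The missing-month, same-year row can date a true post-vaccination AE before dosing, and SAP 10.1.1 then keeps it out of the summaries built on AE-page start dates. Neither document overrides this.

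Among same-year AEs with this date pattern, about 9% (onset Days 0-6) to 45% (onset flat over Days 0-180) would be misplaced, if dose dates are spread evenly over a year and the exclusion uses the imputed date. These are conditional shares and do not estimate how many events the trial would lose. The mechanism is certain on the text; the size is not.

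**What to change.** Add to the missing-month, same-year start-date row of Table 2, for AEs only:

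> If the resulting date is before the dose date, or is not a valid calendar date, and the recorded stop date does not show that the event ended before dosing, set the start date to the dose date.

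Leave the other rows unchanged. A floor at the dose date across the whole table would be wrong. With a June dose, an ongoing AE recorded as starting in May of that year, day unknown, is known to be pre-dose; a general floor would turn it into a post-vaccination event, and likewise a start known only to be in the previous year. Such events can be on file, because Protocol 9.1.2 records occurrences between consent and dosing on the AE form.

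The cost is one SAP sentence and one line of code. There is a small downside: an occasional true pre-dose AE with an unknown month may be counted as post-vaccination, which is the conservative direction for safety.
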